12.4 Assessment of Safety

Any subject that receives at least one dose of treatment on this protocol will be evaluated for toxicity. Drug toxicity will be defined using the National Cancer Institute (NCI) Common Terminology Criteria for Adverse Events (CTCAE), version 5.0.

12.5 Assessment of Efficacy

Efficacy will be determined at the time of prostatectomy, 6 months after drug initiation, by the rate of response. Response is defined by the combined rate of pathologic complete response (pCR) and minimal residual disease (MRD), as defined by residual tumor <5 mm in cross section.

12.6 Data Analysis Plans

Success rates and corresponding confidence intervals will be computed for primary, secondary and exploratory variables. Descriptive statistics, such as mean, median, SD, min and max, will be provided for continuous variables, and contingency tables will be provided for pairs discrete variables. Kaplan-Meier methodology will be used to estimate BCR-free survival. Two year biochemical recurrence-free survival and rate of PSA₀ (undetectable PSA with testosterone recovery and no additional therapy) will be computed. Data will be analyzed by the study statistician using ***R*** and ***Stata*** software.

12.6.1 Analysis Plans for Primary Objective

The primary endpoint is ***the response rate***. This is the combined rate of pathologic complete response (pCR) and minimal residual disease (MRD), as defined by residual tumor <5 mm in cross section. Point estimator and 95% confidence interval will be provided.

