2.2 Endpoints

2.2.1 Primary Endpoint

- Combined rate of pathologic complete response (pCR) (defined as absence of pathologic disease on hematoxylin and eosin (H&E) stain (ypT0)), or with presence of minimal residual disease (<5 mm linearly)

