3.2 Eligibility Criteria for Phase II Neoadjuvant Cohort

3.2.1 Phase II Inclusion Criteria

Subject must meet all of the following applicable inclusion criteria to participate in this study:

1. Histologically-confirmed diagnosis of localized, untreated prostate cancer with high-risk features. High-risk features is defined as:
 - Two or more cores from prostate biopsy that are grade group 4 (Gleason score 4+4=8) or higher,
 - OR**
 - Stage T3-4 (by clinical exam or MRI), M0, and at least 2 cores from prostate biopsy that are grade group 3 (Gleason score 4+3=7) or higher.
- NOTE:** Pathology confirmation of malignancy must be performed by the participating site (i.e. reports should be issued by the participating site; if a subject's pathology report was not issued by the participating site, archival tissue should be requested by the participating site for internal pathology review.)
2. Sufficient archival tissue (at least 2 cores) available for targeted sequencing and immunohistochemistry to evaluate for PTEN loss using the Ventana SP218 immunohistochemistry assay at the local institution.
 - The tumor evaluated for PTEN expression should be selected based on containing both high grade and high volume of tumor content. The slide evaluated for PTEN expression should be saved for confirmatory central review. Eligibility is based on local review.
3. Measurable PSA
4. Must have PTEN loss per local institution evaluation, defined as 50% or more of tumor tissue being negative for PTEN expression on Ventana SP218 immunohistochemistry assay.
5. Disease must be untreated and subject must be eligible for (per PI discretion) and planning to undergo radical prostatectomy.
6. Male and ≥ 18 years of age.
7. ECOG performance status of ≤ 1 within 14 days prior to signing consent.
8. CT or MRI of abdomen and pelvis and bone scan within ≤ 90 days prior to starting study drug.
9. Able to swallow pills

10. Must have ability to understand and the willingness to sign a written informed consent prior to starting study drug.
11. Sexually active patients, unless surgically sterile, must agree to use effective barrier method and refrain from sperm donation during the study treatment and for 3 months after the end of study treatment.
12. As determined by the enrolling physician or protocol designee, ability of the subject to understand and comply with study procedures for the entire length of the study

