8.1.2 Phase II Neoadjuvant cohort

Prostate biopsy - Archival tissue must be available to evaluate for PTEN loss locally using the Ventana SP218 immunohistochemistry assay. Central review to confirm PTEN loss will be performed retrospectively. If and when funding becomes available, additional studies may include immunohistochemical (IHC) analysis (such as evaluation of expression of hormone receptors, markers of proliferation, and neuroendocrine markers), as well as extraction and evaluation of DNA and RNA for genetic analysis.

Prostatectomy specimen - Once the prostatectomy specimen has been evaluated for clinical purposes, tissue is required for central review and correlative studies. If there is more than minimal residual disease on a single block, a block representative of the residual disease is requested to be used for exploratory studies, as well as a corresponding H&E slide. If and when funding becomes available, these studies will include immunohistochemical (IHC) analysis (such as evaluation of expression of hormone receptors, markers of proliferation, neuroendocrine markers, and immune markers), as well as extraction and evaluation of DNA and RNA for genetic analysis. If there is a pathological complete response (pCR) or minimal residual disease (MRD) by local review, slides from each block are requested for central review.

Blood/plasma for immunogenicity studies and ctDNA - Blood will be collected Cycle 1 Day 1, Cycle 2 Day 1, and Cycle 6 Day 1. Analysis to be performed upon receipt of funding.

Blood for somatic baseline - Whole blood will be collected prior to C1D1 treatment for somatic baseline comparison.

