9. CRITERIA FOR DISEASE EVALUATION

9.1 Phase II Neoadjuvant cohort

9.1.1 Pathological response

Response for the Phase II neoadjuvant cohort will be evaluated at the time of prostatectomy. Those with pathological complete response (absence of pathologic disease on hematoxylin and eosin (H&E) stain (defined as ypT0)), or with presence of minimal residual disease (<5 mm linearly), will be considered to be responders. Those with more than minimal residual disease will be considered to have no response.

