12.3 Sample Size and Accrual

In this Simon MiniMax two-stage, single arm, phase I/II trial, we anticipate enrolling 17 evaluable PTEN-negative subjects in the primary analysis (phase II) cohort. The therapy will be considered to be of little interest in the neoadjuvant setting if the exceptional response rate is $<5\%$ (similar to AR-targeted therapy alone) and considered active if the exceptional response rate is $\geq30\%$. The study is designed with 90.5% power to detect the difference between the null hypothesis (5% or less response rate) and the alternative hypothesis (30%) with one-sided type I error of 0.05. In the first stage nine (9) patients will be recruited. If one (1) or more responses (pCR or MRD) are observed, another eight (8) evaluable patients will be recruited for a total of 17 evaluable patients. If 3 or more of 17 responses are observed, the study will be deemed a success. To account for 15% attrition, we plan to enroll 20 patients.

The Phase I de-escalation cohort will consist of patients with metastatic or nonmetastatic castrate resistant prostate cancer, with the expected sample size of 6, ***assuming no more than 1 DLT in the first 6 patients***. However, if dose reductions of ipatasertib are required, the sample size could be as large as 18.

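### Do two wordings of minimal residual disease, and no named deciding reader, leave the primary endpoint undefined?

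*Combined protocol and SAP*

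**What the plan says.** Minimal residual disease (MRD) is described in five places in the combined protocol and SAP.

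- Section 2.2.1 counts complete response "or with presence of minimal residual disease (<5 mm linearly"), and Section 12.2.1 repeats this. Section 9.1.1 uses the same measure to classify patients: "or with presence of minimal residual disease (<5 mm linearly), will be considered to be responders".
- Section 12.5 has "and minimal residual disease (MRD), as defined by residual tumor <5 mm in cross section", and Section 12.6.1 repeats it for the primary analysis: "minimal residual disease (MRD), as defined by residual tumor <5 mm in cross section".

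On who reads the specimen, Section 8.1.2 starts from the clinical evaluation and says that tissue from the prostatectomy is required for central review and correlative work. Where the result is complete response or "minimal residual disease (MRD) by local review, slides from each block are requested for central review". Where more than minimal disease remains, "a block representative of the residual disease is requested to be used for exploratory studies", together with a matching H&E slide. For PTEN status, by contrast, Section 3.2.1 names the deciding reader outright: "Eligibility is based on local review".

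The count feeds two rules. Section 12.7.2 halts accrual if none of the first 9 evaluable men responds. Section 12.3 states the final rule: "If 3 or more of 17 responses are observed, the study will be deemed a success".

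**The concern.** A linear extent and a cross-section could be taken as different dimensions. A thin focus running through several blocks might then be small on each section yet exceed 5 mm in total length, and be a responder under one wording only. The plan gives no rule for several foci or for a focus that crosses blocks.

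The plan also settles local against central reading for PTEN but has no matching sentence for response. Slides from every block are requested only for local responders, so a central re-read might seem able to remove responders but hardly to add them. Finally, men with N1 disease are eligible, while complete response is labelled ypT0 with no mention of nodes.

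In an unblinded single-arm trial of 17 men, an endpoint that could be settled after the specimens are seen would put the go/no-go verdict in doubt.

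**Working it through.** **1. Do the design figures hold?** Inputs from Section 12.3: p0 = 0.05, p1 = 0.30, 9 men then 8 more, continue with at least 1 response, success with at least 3 of 17. With X1 ~ Bin(9, p) and X2 ~ Bin(8, p) independent,

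P(success) = P(X1=1)·P(X2≥2) + P(X1=2)·P(X2≥1) + P(X1≥3).

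- p = 0.05: 0.29854 × 0.05724 + 0.06285 × 0.33658 + 0.00836 = 0.01709 + 0.02115 + 0.00836 = **0.0466**, within the stated 0.05.
- p = 0.30: 0.15565 × 0.74470 + 0.26683 × 0.94235 + 0.53717 = 0.11591 + 0.25145 + 0.53717 = **0.9045**, the stated 90.5%.

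**2. How often would one specimen matter?** The probability of passing stage 1 and ending one step either side of the line:

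| | p = 0.05 | p = 0.30 |
|---|---|---|
| X1≥1 and X = 2 | 0.1251 | 0.0461 |
| X1≥1 and X = 3 | 0.0380 | 0.1143 |
| Sum | 0.1631 | 0.1604 |

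The sum mixes two directions. An upgrade matters only at X = 2 and a downgrade only at X = 3. If the central re-read mainly removes responders, only the second row applies: 3.8% and 11.4%.

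**3. What are the bounds for one reversal?** The documents give no discordance rate, so these figures suppose that one specimen is reversed in every trial where that is possible.

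- Upgrade after stage 1 is passed: type I error 0.0466 + 0.1251 = 0.1717. Upgrade within stage 1: P(X≥2 of 17) = 0.208.
- Downgrade with stage 1 unaffected: power 0.9045 − 0.1143 = 0.790 (from unrounded values). Downgrade within stage 1, which then needs X1≥2 and X≥4: power 0.720.

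These bounds show what a true misclassification could cost. They are not evidence that the wording causes one.

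**4. Do the wordings conflict?** Both set a limit of 5 mm, which is a length and not an area or volume. Pathology measures residual tumor on cut sections, so the linear extent seen on a section meets both descriptions. A conflict arises only if *linearly* is taken to mean a length rebuilt across blocks, which no section asks for.

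**5. Which reading counts?** Section 9.1.1 evaluates response at the time of prostatectomy. Section 12.5 determines efficacy at that same point. Section 12.7.2 refers to pathologic evaluation of the 9th prostatectomy. Section 8.1.2 puts the clinical evaluation first and makes the all-block slide request depend on its result. Together these point to the local reading as the endpoint, with central review as confirmation.

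**6. Is the slide request lopsided?** One block with too much tumor is enough to show non-response. Complete response or MRD can be confirmed only by looking at every block. The difference in requests follows from what each claim needs as proof, and Section 8.1.2 still requires tissue from every specimen for central review.

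**7. Nodes.** The endpoint as stated is ypT0 or residual tumor under 5 mm. Nodal status is not part of it, so a positive node does not alter the classification.

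**The case for a change.** The best case for acting is that the cost is small and the verdict is a count. One agreed phrase in five sections and one sentence naming the reader would remove any argument, and the authors wrote such a sentence for PTEN. The boundary is also more exposed at rates between the two design points: the chance of ending at exactly 2 or 3 responses after passing stage 1 is 36.5%, 42.9% and 37.2% at true rates of 10%, 15% and 20%.

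Some of this stands. The equivalence of the wordings is nowhere stated, the local reading is inferred and not declared, and several foci are not addressed. But a one-patient boundary exists under any threshold rule, so these percentages describe a small trial and not a faulty definition. None of them shows that following the plan as written gives a wrong classification. Harmonising the text would be tidy, and it would leave the sample size, the thresholds and the error rates where they are.

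**Conclusion.** The concern does not call for a change. The difference between Sections 2.2.1, 9.1.1 and 12.2.1 on one side and 12.5 and 12.6.1 on the other is most likely a clerical variation on one 5 mm linear measure. The deciding reader is missing detail that the surrounding sections answer well enough: the local reading at prostatectomy supplies the count, and central review can be reported beside it.

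The design stands at 4.7% type I error and 90.5% power. The bounds of 17.2% to 20.8% for type I error and 72.0% to 79.0% for power apply only if one specimen is reversed in every trial where that is possible, and nothing in the documents supports such a rate.

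This rests on two readings that the plan supports but does not spell out: that the linear extent is taken on the section, and that the local evaluation feeds the 0 of 9 and 3 of 17 rules.

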12.6.2 Analysis Plans for Secondary Objectives

For secondary endpoints, descriptive statistics will be given for rates of toxicity and rates of PSA₀. Kaplan-Meier methodology will be used to estimate BCR-free survival, with 95% confidence envelope around the survival curve.

12.6.3 Analysis Plans for Exploratory Objectives

For exploratory endpoints descriptive statistics will be used to evaluate the mean, median, SD and the range of observed values.

12.7 Interim Analysis/Criteria for Stopping Study

12.7.1 Phase I (De-escalation Cohort)

The study will be terminated if there are 2 or more DLTs at dose level -2 (darolutamide 600 mg BID and ipatasertib 200 mg daily) and will not proceed to Phase II.

12.7.2 Phase II (Neoadjuvant Cohort)

In the Phase II neoadjuvant cohort, if after 9 evaluable patients there are no patients with exceptional response (defined as pCR or MRD), accrual will halt due to lack of efficacy. Accrual will not pause while the 9th patient is on therapy, so additional patients may accrue prior to pathologic evaluation of the 9th radical prostatectomy.

For the Phase II neoadjuvant cohort, an additional *early stopping rule for safety* will also be followed throughout the duration of the study. If, at any time, 2 or more patients experience a delay in time to prostatectomy of >28 days after the final dose of ipatasertib (i.e., a delay of > 1 week beyond the allowed timeline of 7-21 days) *due to an ipatasertib-related AE*, the study and all study treatment will be stopped. An ipatasertib-related AE is defined as an AE that is possibly, probably, or definitely related to ipatasertib. Should the study stop early, discussion of reopening the study using modified ipatasertib treatment regimens may be considered after discussion between the PI and Genentech, and after approval by the DSMC.

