STATISTICAL CONSIDERATIONS	
In this Simon MiniMax two-stage, single arm, phase I/II trial, we anticipate enrolling 17 evaluable PTEN-negative subjects in the Phase II neoadjuvant cohort. The therapy will be considered to be of little interest in the neoadjuvant setting if the exceptional response rate is <5% (similar to AR-targeted therapy alone) and considered active if the exceptional response rate is $\geq 30\%$. The study is designed with 90.5% power to detect the difference between the null hypothesis (5% or less response rate) and the alternative hypothesis (30%) with one-sided type I error of 0.05. In the first stage nine (9) patients will be recruited. If one (1) or more responses (pCR or MRD) are observed, another eight (8) evaluable patients will be recruited for a total of 17 evaluable patients. If 3 or more of 17 responses are observed, the study will be deemed a success. To account for 15% attrition, we plan to enroll 20 patients.
 
The Phase I de-escalation cohort will consist of patients with metastatic or nonmetastatic castrate resistant prostate cancer, with the expected sample size of 6, assuming no more than 1 DLT in the first 6 patients. However, if dose reductions of ipatasertib are required, the sample size could be as large as 18.

TOTAL NUMBER OF SUBJECTS	N = 26-38 (Phase I de-escalation cohort = 6-18; Phase II neoadjuvant cohort = 20)
ESTIMATED ENROLLMENT PERIOD	12 months
ESTIMATED STUDY DURATION	42 months

TABLE OF CONTENTS

Schema: Phase I De-escalation cohort	8
Schema: Phase II Neoadjuvant Cohort	9
1. Background and Rationale	10
1.1 High risk localized prostate cancer	10
1.2 Neoadjuvant intensive androgen deprivation.....	10
1.3 The pan-AKT inhibitor Ipatasertib	10
1.4 Rationale	11
2. Study Objectives and Endpoints	11
2.1 Objectives	11
2.2 Endpoints	11
3. Eligibility Criteria	12
3.1 Eligibility Criteria for Phase I de-escalation cohort	12
3.2 Eligibility Criteria for Phase II Neoadjuvant Cohort	14
4. Subject Registration	16
5. Treatment Plan	16
5.1 Phase I de-escalation cohort	17
5.2 Phase II Neoadjuvant cohort	18
5.3 Ipatasertib, Darolutamide and ADT Administration	19
5.4 Concomitant Medications	19
5.5 Supportive Care	21
6. Toxicities and Dose Delays/Dose Modifications	21
6.1 Dose Delays/Dose Modifications	23
6.2 Darolutamide Dose Modifications	23
6.3 Ipatasertib Dose Levels for Dose Reductions	23
6.4 Protocol Therapy Discontinuation	30
6.5 Protocol Discontinuation	31

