5.2 Phase II Neoadjuvant cohort

The single arm, two stage Phase II neoadjuvant portion of the trial will examine the recommended dose of ipatasertib with darolutamide in the neoadjuvant setting, selected for patients with loss of PTEN by IHC. If after 9 evaluable patients there are no patients with exceptional response (defined as pCR or MRD), accrual will halt due to lack of efficacy. Accrual will not pause while the 9th patient is on therapy; additional patients may accrue prior to pathologic evaluation of the 9th radical prostatectomy. Patients in the Phase II neoadjuvant cohort will continue on therapy for 6 cycles.

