13.3 DSMC Review of Safety Data

The Sponsor Investigator and the study team will review all available safety data prior to making dose de-escalation decisions. Once a decision has been reached, the official decision and the supporting safety data will be submitted to the NU DSMC. Treatment of additional subjects may not proceed until the DSMC approves the dosing decision for the next stage. This process will also apply during any interim analyses.

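### Does open accrual during the stage-1 futility look, with no explicit rule for men enrolled beyond the ninth, undermine the two-stage design?

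*Combined protocol and SAP*

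**What the plan says.** Section 12.3 sets out a Simon two-stage design with a null response rate of 5%, an alternative of 30%, one-sided type I error of 0.05 and 90.5% power. Nine men come first. Then: "If one (1) or more responses (pCR or MRD) are observed, another eight (8) evaluable patients will be recruited", which makes 17. The final rule is: "If 3 or more of 17 responses are observed, the study will be deemed a success". Twenty men are enrolled to allow for 15% attrition.

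Sections 5.2 and 12.7.2 give the futility action: with no responder among 9 evaluable men, accrual halts for lack of efficacy. Both say that accrual stays open in the meantime. Section 5.2 has "Accrual will not pause while the 9th patient is on therapy; additional patients may accrue", and section 12.7.2 has "Accrual will not pause while the 9th patient is on therapy, so additional patients may accrue prior to pathologic evaluation".

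Section 13.3 describes how the study team takes dose de-escalation decisions to the DSMC. It says "Treatment of additional subjects may not proceed until the DSMC approves the dosing decision for the next stage" and ends "This process will also apply during any interim analyses".

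The synopsis entry "ESTIMATED ENROLLMENT PERIOD" is 12 months, not split between phases, and the estimated study duration is 42 months.

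**The concern.** Three things look wrong on a first reading.

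- **Who may start, and when.** Section 12.3 reads as if the second eight men are recruited only after a response is seen. Sections 5.2 and 12.7.2 let men enter before that is known. Section 13.3 seems to bar treating further men until the DSMC has acted. No section says how the three fit together.
- **How the extra men count.** If the first nine men all fail, several others will already be on treatment. The plan does not call 0 of 9 final, and the 3-of-17 sentence, taken alone, carries no condition on stage 1. A team with 0 of 9 and late responders might be tempted to claim success.
- **What the stop achieves.** A two-stage design is normally chosen to limit the number of patients given an inactive regimen, here before potentially curative surgery. The endpoint takes about six months to observe, so open accrual could fill most of the cohort before the look.

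At stake would be the type I error rate, an efficacy conclusion left open to choice after the data are seen, and a safeguard weaker than section 12.3 suggests.

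**Working it through.** **1. Reproduce the stated power.** Inputs from section 12.3: 9 men in stage 1, stop at 0 responders; 8 more in stage 2; success at 3 or more of 17; response rates p = 0.05 and p = 0.30.

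With 0 of 9 final,

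P(success) = Σ over x = 1 to 9 of P(X₁ = x) × P(X₂ ≥ 3 − x), with X₁ ~ Bin(9, p) and X₂ ~ Bin(8, p).

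- p = 0.05: 0.2985 × 0.0572 + 0.0629 × 0.3366 + 0.0084 = 0.0466.
- p = 0.30: 0.1556 × 0.7447 + 0.2668 × 0.9424 + 0.5372 = 0.9045.

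The three terms are one responder, two responders, and three or more responders in stage 1. The result matches the stated 90.5% and keeps alpha below 0.05.

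**2. Ignore the stop and count everyone.** P(Bin(17, p) ≥ 3) is 0.0503 at p = 0.05 and 0.9226 at p = 0.30. The difference between the two rules is the probability of 0 of 9 followed by at least 3 of 8:

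| Response rate | P(0 of 9) | P(≥ 3 of 8) | Product |
|---|---|---|---|
| 5% | 0.6302 | 0.0058 | 0.0036 |
| 20% | 0.1342 | 0.2031 | 0.0273 |
| 30% | 0.0404 | 0.4482 | 0.0181 |

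The 0.9226 does not match the stated power, so the sample-size calculation itself treats 0 of 9 as final.

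**3. How many men are enrolled at the look.** Inputs:

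- Treatment lasts 6 × 28 = 168 days.
- Surgery follows by one of two windows: 7–21 days after the last ipatasertib dose (section 12.7.2), or 28 ± 14 days after cycle 6 (section 7, Phase II calendar footnote 3). The windows differ and need reconciling as a separate matter; both are used here, so the lag is 168 + 7 = 175 to 168 + 42 = 210 days.
- The ninth evaluable man is the 9th enrolled with no attrition, or the 9/0.85 = 10.6th with 15%.
- Assumption: the 20 Phase II men arrive evenly over the accrual period, and no time is added for reading the specimen or for DSMC review.

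Look day = k × (accrual days / 20) + lag. Enrolled = min(20, look day ÷ (accrual days / 20)).

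For 12 months the gap between men is 365.25/20 = 18.26 days. The earliest look is 9 × 18.26 + 175 = day 339, with 339.4/18.26 = 18.6 men enrolled. The latest is 10.59 × 18.26 + 210 = day 403, with all 20 enrolled.

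| Accrual of 20 men | Look day | Enrolled | Not yet enrolled |
|---|---|---|---|
| 12 months | 339–403 | 18.6–20 | 0–1.4 |
| 18 months | 421–500 | 15.4–18.3 | 1.7–4.6 |
| 24 months | 504–597 | 13.8–16.3 | 3.7–6.2 |

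The 18- and 24-month rows are assumptions that show the range. For comparison, a design that pauses would treat 9 + 8 × (1 − 0.6302) = 12.0 evaluable men on average at a 5% response rate.

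**4. What a pause would cost.** Holding accrual from the ninth evaluable man's first dose to his result takes 175–210 days, about 5.7–6.9 months. The 42-month duration equals 12 months of enrollment + 6 months to prostatectomy (section 12.5) + 24 months of follow-up (section 7.2), so it contains no such hold.

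**5. Put the sections in time order.** Sections 5.2 and 12.7.2 cover the period before the ninth specimen is read: accrual is open. Section 13.3 takes effect when there is a decision to submit, so at the futility look it applies once the stage-1 result exists. Section 12.3 describes the decision rule. Applied in that order, the three do not contradict one another.

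**The case for a change.** The strongest case for a change is that the time order in step 5 is inferred, not written. A site with a consented man ready to start on the day the ninth specimen is read would have to ask whether he may begin. The extra men are also foreseeable: at a 5% response rate the stop is triggered 63% of the time, and other men will nearly always be on treatment when it is. Their status could be fixed in one sentence before data exist, at no cost. Counting them takes alpha just past 0.05. And although sections 5.2 and 12.7.2 disclose that men may accrue early, they do not say that this could be nearly the whole cohort.

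Much of this stands as fact: the text is silent on these points, and a clarifying sentence would do no harm. It does not show that the plan leads an analyst wrong. The named design, the order of the sentences in section 12.3, the halt for lack of efficacy and the stated power all lead to one reading. The excess of alpha over 0.05 is 0.0003, and it arises only if that reading is abandoned. On starting new men after the result, section 13.3 already sends the decision to the DSMC. On exposure, the plan promises no particular saving, and the size of the overrun depends on an accrual period that is labelled an estimate and not divided between phases. PTEN loss, an entry requirement, is put at about 20% of localized cancers in section 1.1, so slower accrual is plausible. If the 12 months also has to cover Phase I, accrual of the 20 men is faster and none are spared.

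**Conclusion.** No change to the plan follows. No stated figure is wrong: power, alpha and the enrollment of 20 (17/0.85) all reproduce. The missing statement about men beyond the ninth is a gap that a statistician would fill in the way the design calculation already does: 0 of 9 is a negative result, and later men are reported descriptively. Filling it the other way would raise alpha by 0.0036 and power by 0.018. The link between sections 12.7.2 and 13.3 is a missing cross-reference, not a contradiction.

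Keeping accrual open is a fair trade-off, stated in two places: roughly six months of trial time is saved, and in return the futility stop spares few men, 0 to 1.4 of 20 under even accrual over 12 months and more if accrual is slower. The stop still settles the efficacy conclusion, and the continuous safety rule in section 12.7.2 and the DSMC reviews in section 13 run independently of it. The error-rate figures are exact for 17 analysed men; the exposure figures rest on the even-accrual assumption and on the two surgery windows in the protocol.
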